6.6 DOSE LIMITING TOXICITIES-PHASE IB COMPONENT

The phase Ib component of the study will consist of 3+3 dose escalation rule with the dose of LEE011 escalating up to 600mg daily to determine the maximum tolerated dose (MTD) that will be used during the phase II component. The dose levels for the phase Ib aspect will be 200 mg, 400 mg, or 600 mg daily.

Only the first cycle of therapy (one cycle equals to one month) will be used to determine dose limiting toxicity (DLT). However, if two total grade 5 adverse events or 2 Grade 4 adverse events (lasting ≥ 7 days); occur at any time while the patient is still receiving study treatment that are either: definitely, probably, or possibly related to either LEE011 or TACE the study will be terminated to enrollment.

Only patients started on the first dose of LEE011 will be included in the evaluation of DLT. If a patient has a DLT that patient will not receive further LEE011. Patients following initial chemoembolization who never receive LEE011 will not be included in the MTD analysis and will be replaced. The patients will be followed for thirty days following the initial chemoembolization for safety assessment. Patients will be enrolled into the next highest drug cohort only after 3 or 6 patients have completed the first cycle of therapy. Once the MTD is determined, patients at the MTD dose will continue with LEE011 and represent the first three patients accrued to the phase II aspect.

Due to observed (TACE related, non DLT) toxicity on cohort 1 specific criteria for cohort 1 has been developed after discussion with the FDA. Cohort 1 has been expanded to 6 patients. Decision for dose escalation will be made using the following criteria:

- No or one DLT: the next three patients will be assigned to next higher dose level (400 mg of LEE011).
- At least two toxicities: the MTD is exceeded and the phase I component of the trial will be stopped with no continuation into the phase II component.

For Cohort 2 and 3 the following traditional 3+3 dose escalation rules will be used:

- If a dose limiting toxicity (DLT) is observed in 1 out of 3 patients at a given dose level, up to 3 additional patients will be enrolled and treated at that dose level.
- If 2 out of 3-6 patients at that dose level have DLTs, the dose will be decreased to the previous dose level, and up to 3 additional patients will be enrolled at that dose level for a total of 6 patients.

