- When up to 3 additional patients are added to a given dose level, if 0-1 of 6 patients has a DLT then the dose will be increased to the next dose level.
- Additional dose levels may be explored per investigator discretion to define the safety profile of the treatment.

The recommended Phase II dose (RP2D) will be the highest cohort level in which one or fewer subjects of 6 develops a first cycle DLT.

The Data and Safety Monitoring Committee as described below will regularly review all serious adverse events and any local adverse events, which are unanticipated problems. The study will utilize the Common Terminology Criteria for Adverse Events (CTCAE) version 4.03 for grading of all adverse events related to treatment.

Table 6.2: Dose-limiting toxicity: phase Ib component

The following will be considered a DLT if they occur within the first cycle of therapy with LEE011 and are determined to be possibly, probably or definitely related to LEE011

Grade 4 neutropenia lasting more than 7 consecutive days
Grade 3 or 4 febrile neutropenia
≥ Grade 3 vomiting ≥ 48 hours despite optimal anti-emetic therapy
≥ Grade 3 diarrhea ≥ 48 hours despite optimal anti-diarrhea therapy
Clinical signs of cardiac disease, such as unstable angina or myocardial infarction, or Troponin ≥ grade 3
Grade 4 serum alkaline phosphatase > 7 days
≥ Grade 3 serum creatinine
≥ Grade 3 adverse event for any non-hematologic toxicity unless otherwise specified as below (excluding alopecia, fatigue < 5 days, laboratory abnormalities that are responsive to oral supplementation or deemed by the investigator to be clinically insignificant).

THROMBOCYTOPENIA	
Toxicity/Grade	Dose Limiting Toxicity and Management Recommendations
Grade 3 ($\geq 25 \times 10^9/L$ - $<50 \times 10^9/L$) without clinically significant bleeding	Dose interruption until recovery to grade ≤ 2 . Re-initiate LEE011 at the same dose level. • If toxicity recurs at grade 3: dose limiting toxicity
Grade 3 ($\geq 25 \times 10^9/L$ - $<50 \times 10^9/L$) with clinically significant bleeding	Dose limiting toxicity
Grade 4 ($<25 \times 10^9/L$)	Dose limiting toxicity

HEPATOTOXICITY (BILIRUBIN, ALT, AST)	
TOTAL BILIRUBIN without ALT/AST increase above baseline value	
Toxicity/Grade	Dose Limiting Toxicity and Management Recommendations
Same grade as baseline or increase from baseline grade 0 to grade 1	Maintain dose level with LFTs monitored every other-week

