12.0 STATISTICAL CONSIDERATIONS

12.1 STUDY DESIGN/STUDY ENDPOINTS

The study is an open-label, non-randomized single-arm, single institution phase Ib/II therapeutic clinical trial. The study population will be patients with advanced hepatocellular carcinoma.

The phase Ib component of the study will consist of a traditional 3+3 dose escalation rule with 3 or 6 patients in each cohort, the process for dose escalation is outline in section 6.4.

The primary endpoint of the phase II component will be progression free survival (PFS) of

HCC patients. PFS is defined to be the time from initiation of treatment to progression or death without evidence of progression. For cases without documentation of progression, follow-up will be censored at the date of last disease assessment without progression, unless death occurs within 4 months following the date of last progression-free, in which case death will be counted as an event. The historical median PFS for TACE alone is 8-10 months. Our institutional median PFS following the TACE protocol outlined is 8.0 months. This study will target a hazard ratio of 0.69 with an 80% power and a one-sided significance level of 10%. Assuming a 24-month accrual and an 18-month follow-up period the study requires 38 patients initiating LEE011 treatment with the median PFS for TACE alone is 8 months, and 40 patients with the median PFS for TACE alone is 10 months. PFS will be estimated using the Kaplan-Meier method, and Greenwood's formula will be used to calculate the standard error of the corresponding Kaplan-Meier estimate and 95% confidence interval. Survival curves will be estimated using Kaplan-Meier methodology. Forty total patients will be enrolled in the phase II aspect of the trial. This includes only patients who undergo chemoembolization and initiate LEE011 therapy.

Secondary endpoints of efficacy are to evaluate OS. The statistical methods used for the analysis of PFS will be used for the analysis of OS.

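### After 0/3 DLTs at 600 mg no rule takes the cohort to 6 patients, so the written RP2D definition cannot select 600 mg

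*Combined protocol and SAP*

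**What the plan says.** Section 6.6 plans three levels: 200, 400 and 600 mg. Cohort 1 (200 mg) has been expanded to 6 patients and escalates on 0 or 1 DLT. For cohorts 2 and 3, patients are added in two situations only:

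- A DLT is "observed in 1 out of 3 patients at a given dose level, up to 3 additional patients will be enrolled".
- A higher level has 2 DLTs, so the dose steps down and "up to 3 additional patients will be enrolled at that dose level for a total of 6 patients".

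The RP2D is then the highest cohort level at which "one or fewer subjects of 6 develops a first cycle DLT". The Study Summary doses phase II at the phase Ib MTD. The protocol gives no definition of the MTD apart from this RP2D sentence.

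Other text bears on the point without settling it:

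- Section 12.1 describes a "3+3 dose escalation rule with 3 or 6 patients in each cohort".
- Section 6.6 says that patients at the MTD "represent the first three patients accrued to the phase II aspect".
- Section 6.6 also says "Additional dose levels may be explored per investigator discretion".
- For the escalation process, section 12.1 states that "the process for dose escalation is outline in section 6.4", but section 6.4 holds only instructions for taking the capsules.

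**The concern.** Neither trigger for adding patients can apply after 0/3 at 600 mg, because there is no single DLT to prompt expansion and no planned level above to step down from. The cohort ends at 3 patients, and a definition written out of 6 cannot be met. A cohort with one DLT in its first 3 patients is expanded, and if it ends at 1/6 it qualifies. A cleaner safety result therefore disqualifies a dose that a worse result would allow.

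This settles what the phase II patients receive. If the rule is applied as written, phase II runs at a lower dose than the data support. If it is set aside, the dose rests on half the patients that the protocol's own definition asks for. Cohort 1 was itself enlarged to 6 after TACE-related toxicity and discussion with the FDA, so the highest dose would be cleared on less evidence than the lowest. The 67 patients at 600 mg reported in section 1.7.4 come from the first-in-human study, without TACE.

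**Working it through.** **Reproducing the stated size.** The Study Summary gives 9-18 phase Ib patients. This matches 3+3+3 = 9 up to 6+6+6 = 18 for an ordinary three-level 3+3. With cohort 1 fixed at 6, trials that reach 600 mg use 6+3+3 = 12 up to 18, and the 12-patient run with no DLTs at 400 or 600 mg leaves 600 mg at 0/3.

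**What the literal rule names after 0/3 at 600 mg.**

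- If 400 mg also showed 0/3, only cohort 1 has 6 patients, so 200 mg is named.
- If 400 mg went from 1/3 to 1/6, it has 6 patients and 1 DLT, so 400 mg is named.

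**Path probabilities.** The documents state no DLT rates, so four sets are assumed for 200/400/600 mg. Let p1, p2, p3 be the rates and q = 1 − p. The grade 4/5 termination rule is ignored. It could close enrollment earlier, so the path probabilities are upper bounds at these rates.

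- Cohort 1 passes: C1 = q1^6 + 6·p1·q1^5
- 600 mg is reached: R = C1·(q2^3 + 3·p2·q2^5)
- 600 mg ends at 0/3: R·q3^3
- 600 mg named, written rule (only through 1/3 then 1/6): R·3·p3·q3^5
- 600 mg named, 0/3 accepted: sum of the previous two lines
- 600 mg named, filled to 6 after 0/3: R·(q3^6 + 6·p3·q3^5)
- 400 mg named on 6 after 600 mg fails: C1·(1 − q3^3 − 3·p3·q3^5)·[q2^3·(q2^3 + 3·p2·q2^2) + 3·p2·q2^5]
- 400 mg named on 6 when 600 mg is 0/3: C1·3·p2·q2^5·q3^3

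| Quantity | 5/5/5% | 5/10/20% | 10/20/30% | 10/25/50% |
|---|---|---|---|---|
| C1 | 0.967 | 0.967 | 0.886 | 0.886 |
| R | 0.942 | 0.876 | 0.628 | 0.531 |
| 600 mg ends at 0/3 | 0.807 | 0.449 | 0.215 | 0.066 |
| 600 mg named, written rule | 0.109 | 0.172 | 0.095 | 0.025 |
| 600 mg named, 0/3 accepted | 0.916 | 0.621 | 0.310 | 0.091 |
| 600 mg named, filled to 6 | 0.911 | 0.574 | 0.264 | 0.058 |
| 400 mg on 6 after 600 mg fails | 0.025 | 0.250 | 0.294 | 0.392 |
| 400 mg on 6, 600 mg at 0/3 | 0.096 | 0.088 | 0.060 | 0.020 |
| 400 or 600 mg on 6, literal reading | 0.230 | 0.510 | 0.448 | 0.436 |

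The last row is the sum of the written-rule 600 mg row and the two 400 mg rows. Worked example at 5/10/20%: R = 0.967 × (0.729 + 0.3 × 0.59049) = 0.876, and the 0/3 path is 0.876 × 0.512 = 0.449.

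**Strength of evidence on 3 against 6 patients.** The one-sided 95% upper bound on the DLT rate is 1 − 0.05^(1/3) = 63% after 0/3 and 1 − 0.05^(1/6) = 39% after 0/6. The probability of accepting a dose once it is reached is q^3 + 3·p·q^5 if 3 patients suffice and q^6 + 6·p·q^5 if 6 are required:

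| True DLT rate | 3 suffice | 6 required |
|---|---|---|
| 20% | 71% | 66% |
| 30% | 49% | 42% |
| 40% | 31% | 23% |

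**The case against.** The best reply is that the authors meant 0/3 at 600 mg to be enough. The design is labelled a traditional 3+3, cohorts may have 3 or 6 patients, the accrual sentence speaks of three patients at the MTD, and the lower end of 9-18 fits 3+3+3. The bullets for cohorts 2 and 3 have no 0/3 rule at 400 mg either, so a reader who escalates from there is already relying on context. A team that saw no DLTs at any level, with real-time review by the phase I team and the DSMC (section 16.0), would hardly name 200 mg. On this view the out-of-6 wording is a ceiling on DLTs, and it governs the RP2D, while phase II is dosed at the MTD.

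Part of this stands. The loose reading is plausible, and under it filling the cohort changes the chance of naming 600 mg by only about 1 to 5 percentage points. The largest contrast needs a flat 5% DLT rate, which the documents do not support. The number 9 is not decisive, because 6+3 under the enlarged cohort 1 gives it too.

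The rest does not remove the problem. Escalation from 0/3 at 400 mg has textual support: section 6.6 lets the next cohort open once 3 or 6 patients have completed cycle 1. No comparable sentence lets 3 patients satisfy the RP2D definition. The MTD has no separate definition to fall back on. Investigator discretion covers extra dose levels, not more patients at 600 mg. Some versions of the 3+3 do fill the MTD cohort to 6, but this protocol does not state that step. Section 3.1 does point correctly to section 6.6, so the wrong reference in section 12.1 is minor, but section 6.6 is where the gap lies. The hints that 3 might suffice contradict the definition and do not resolve it.

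**Conclusion.** The concern holds. As written, 600 mg can be the RP2D after 1/6 but not after 0/3. This is a stated rule with an inverted result, not merely a missing detail. Only trials that see 0/3 at 600 mg are affected. At the assumed rates that is at most 81, 45, 22 and 7% of trials, and most often when the combination is well tolerated.

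The size depends on the reading. Taken literally, the chance of naming 600 mg falls from 91, 57, 26 and 6% (cohort filled to 6) to 11, 17, 10 and 2%. Taken loosely, the cost is weaker evidence: an upper bound of 63% in place of 39%, and a dose with a true 30% DLT rate accepted 49% rather than 42% of the time.

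The phase II dose reductions (section 6.7), DSMC review and the rule that ends enrollment "if two total grade 5 adverse events or 2 Grade 4 adverse events" (the latter lasting at least 7 days and at least possibly related to treatment) limit harm to patients. None of them says which dose is named. The sponsor should settle this before cohort 3 is read out.

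**What to change.** Add to section 6.6: *After 0/3 DLTs at 600 mg, 3 more patients are enrolled at 600 mg. 600 mg is the RP2D only if at most 1 of the 6 has a DLT; with 2 or more, de-escalate and fill 400 mg to 6 under the existing rule.* In the accrual sentence, replace the three patients with all patients treated at the RP2D. Correct the cross-reference in section 12.1 to section 6.6.

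The cost is up to 3 more phase Ib patients and about one more DLT window. A clean run becomes 6+3+6 = 15 patients instead of 12. The maximum stays at 18, so both are within the stated 9-18. Under the revised accrual sentence the added patients can count toward the 40 in phase II if 600 mg is selected.

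If 3 patients were truly intended to suffice, adding 0 of 3 at 600 mg to the RP2D sentence would also remove the contradiction and needs no extra patients, but it accepts the weaker evidence shown above. Filling the cohort applies the protocol's own 6-patient standard and is preferable.

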1.7.4 Clinical Safety of LEE011

Please see investigator's brochure for up to date details on LEE011. As of June 15, 2015, 157 patients have been treated with LEE011 in the first-in human phase I study (CLEE011X2101). Patients with advanced solid tumors or lymphomas were treated with increasing doses of LEE011 orally, once daily for 21 days followed by a 1-week rest (28-day cycle).

Evaluation of safety, tolerability, and PK from patients with advanced solid tumors and lymphoma in the FIH study was used to define the MTD and recommended dose for future development. The MTD was determined as 900 mg/day on a 3-weeks-on/1-week-off schedule. The recommended dose for further studies based on the expansion cohort is 600 mg/day with a 3 weeks on/1 week off schedule, which has an acceptable safety profile, lower risk for QTcF prolongation, adequate exposures, and preliminary evidence of clinical activity. The most common hematologic and non-hematologic adverse events are in Tables 2-1 and 2-2.

Table 2-1 Hematologic AEs in study CLEE011X2101

Adverse Event, n (%)		LEE011, 600 mg/day, 3 week on/1 week off schedule (n=67)
Neutropenia	All	22 (33%)
	Grade 3/4	15 (22)
Leukopenia	All	14 (21)
	Grade 3/4	7 (10)
Thrombocytopenia	All	13 (19)
	Grade 3/4	7 (10)
Anemia	All	16 (24)
	Grade 3/4	2 (3)
Lymphopenia	All	10 (15)
	Grade 3/4	8 (12)

Table 2-2 Non-hematologic AEs in study CLEE011X2101

Adverse Event, n (%)		LEE011, 600 mg/day, 3 weekon/1 week off schedule (n=67)
Fatigue	All Grade 3/4	20 (30) 0
Nausea	All Grade 3/4	32 (48) 1 (2)
Vomiting	All Grade 3/4	19 (28) 0
Diarrhea	All Grade 3/4	19 (28) 2 (3)
QT prolongation	All Grade 3/4	10 (15) 0

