6.5 TREATMENT DURATION

Patients will receive trial treatment until one of the following criteria applies:

- disease progression,
- unacceptable toxicity or toxicity that results in treatment interruption of >4 weeks,
- patient experiences DLT

- patient decides to withdraw from study, starts a new therapy or is lost to follow up
- discontinuation from the study treatment for any other reason.
- PI or study sponsor discretion

Patients who come off therapy will be followed for survival regardless of cause of treatment discontinuation.”

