6.7 LEE011 DOSE MODIFICATION GUIDELINE- PHASE IB CYCLE 2+ AND PHASE II COMPONENTS

Management of severe or intolerable adverse reactions requires temporary dose reduction and/or interruption of LEE011 therapy. Refer to Table 6.3 for guidance. Dose increases once LEE011 has been reduced are not allowed.

Table 6.3 Dose Modification Guidelines

Dose Level	LEE011	
	Dose	Number of capsules & strength
Highest dose (0)	600 mg	3 x 200 mg capsules
First dose reduction (-1)	400 mg	2 x 200 mg capsules
Second dose reduction (-2)	200 mg	1 x 200 mg capsules
Third dose reduction (-3)	Discontinue Treatment of LEE011	

Recommendations for dose reduction, interruption, of discontinuation of LEE011 in the management of adverse reactions are summarized in Table 6-4, Table 6-5, Table 6-6, and Table 6-7. Clinical judgment and discretion of the treating physician should guide the management plan of each patient based on individual benefit and risk assessment.

**Table 6-4 LEE011 Dose Adjustment and Management Recommendations for
HEMATOLOGICAL ADVERSE REACTIONS**

THROMBOCYTOPENIA	
Toxicity/Grade	Dose Adjustment and Management Recommendations
Grade 1 ($\geq 75 \times 10^9/L$)	No dose adjustment required.
Grade 2 ($\geq 50 \times 10^9/L - <75 \times 10^9/L$)	No dose adjustment required.
Grade 3 ($\geq 25 \times 10^9/L - <50 \times 10^9/L$)	Dose interruption until recovery to grade ≤ 2 . Re-initiate LEE011 at the same dose level. If toxicity recurs at grade 3: discontinue LEE011
Grade 4 ($<25 \times 10^9/L$)	Discontinue LEE011.

Toxicity/Grade	Dose Adjustment and Management Recommendations
Absolute neutrophil count (ANC)	
Grade 1 ($\geq 1.5 \times 10^9/L$)	No dose adjustment required.
Grade 2 ($\geq 1.0 - < 1.5 \times 10^9/L$)	No dose adjustment required.
Grade 3 ($\geq 0.5 - < 1.0 \times 10^9/L$)	Dose interruption until recovery to $\geq 1.0 \times 10^9/L$. Re-initiate LEE011 at the same dose level. 
 If toxicity recurs at grade 3: temporary dose interruption until recovery to $\geq 1.0 \times 10^9/L$ and reduce LEE011 dose to the next lower dose level.
Grade 4 ($< 0.5 \times 10^9/L$)	Dose interruption until recovery to $\geq 1.0 \times 10^9/L$. Re-initiate LEE011 at the next lower dose level. 
 If toxicity recurs at grade 4: temporary dose interruption until recovery to $\geq 1.0 \times 10^9/L$ and reduce LEE011 at the next lower dose level.
Febrile Neutropenia	

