Grade 3 ANC $< 1.0 \times 10^9/L$ with [a single temperature of $> 38.3^\circ C$ ($101^\circ F$) or a sustained temperature of $\geq 38^\circ C$ ($100.4^\circ F$) for more than one hour]	Dose interruption until improvement of ANC $\geq 1.0 \times 10^9/L$ and no fever. Restart at the next lower dose level. 
 If febrile neutropenia recurs, discontinue LEE011.
Grade 4 Life-threatening consequences; urgent intervention indicated	Discontinue LEE011.
Anemia (Hemoglobin)	
Grade 1 (≥ 10.0 g/dL)	No dose adjustment required.
Grade 2 ($\geq 8.0 - < 10.0$ g/dL)	No dose adjustment required.
Grade 3 (< 8.0 g/dL)	Dose interruption until recovery to grade ≤ 2 . Re-initiate LEE011 at the same dose.

Grade 4 Life-threatening consequences; urgent intervention indicated	Discontinue LEE011.
---	---------------------

**Table 6-5 LEE011 Dose Adjustment and Management Recommendations for
HEPATIC ADVERSE REACTIONS**

HEPATOTOXICITY (BILIRUBIN, ALT, AST)	
TOTAL BILIRUBIN without ALT/AST increase above baseline value	
Grade	Dose Adjustment and Management Recommendations
Same grade as baseline or increase from baseline grade 0 to grade 1	Maintain dose level with LFTs monitored every other-week
Increase from baseline grade 0 or 1 to grade 2 (1.5-3.0 x ULN) or from baseline grade 2 to grade 3 (>3.0 -10 x ULN)	Dose interruption of LEE011 If resolved to \leq grade 1 in \leq 21 days, then maintain dose level If resolved to \leq grade 1 in $>$ 21 days or toxicity recurs, discontinue LEE011

Increase from baseline grade 0 or 1 to grade 3 (>3.0-10 xULN)	Discontinue LEE011
Grade 4 (> 10.0 x ULN)	Discontinue LEE011

Confounding factors and/or alternative causes for increase of total bilirubin should be excluded before dose interruption/reduction. They include but are not limited to: evidence of obstruction, such as elevated ALP and GGT typical of gall bladder or bile duct disease, hyperbilirubinemia due to the indirect component only (i.e. direct bilirubin component ≤ 1 x ULN) due to hemolysis or Gilbert Syndrome, pharmacologic treatment, viral hepatitis, alcoholic or autoimmune hepatitis, other hepatotoxic drugs.
 
For patients with Gilbert Syndrome, these dose modifications apply to changes in direct bilirubin only. Bilirubin will be fractionated if elevated.
	
HEPATOTOXICITY (BILIRUBIN, ALT, AST)	
AST or ALT without bilirubin elevation > 2 x ULN	
AST or ALT Toxicity/Grade	Dose Adjustment and Management Recommendations

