9.0 ADVERSE EVENTS

9.1 LEE001 TREATMENT RELATED EVENTS

The following grade 3 and 4 AEs are suspected to be related to LEE011 treatment for reporting purposes:

- Anemia, febrile neutropenia, leukopenia, lymphopenia, neutropenia, thrombocytopenia;
- Electrocardiogram QT prolonged, hypertension;
- Diarrhea, nausea, vomiting, stomatitis, mucositis; abdominal pain;
- Pneumonia
- Asthenia/fatigue; decreased appetite
- Hepatocellular injury; Hepatic function abnormalities (elevated transaminases); elevated creatinine
- Rash;
- Hyponatremia

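### An isolated LEE011-related grade 4 anemia in phase Ib cycle 1 is not a DLT under Table 6.2, although Table 6-4 ends LEE011 for the same event from cycle 2 on and in phase II

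*Combined protocol and SAP*

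**What the plan says.** Section 6.6 counts a DLT only if it occurs in the first cycle and is possibly, probably or definitely related to LEE011. Table 6.2 has three hematologic entries: grade 4 neutropenia lasting more than 7 days, "Grade 3 or 4 febrile neutropenia", and a thrombocytopenia block. The general row for events of grade 3 or higher reads "Grade 3 adverse event for any non-hematologic toxicity unless otherwise specified as below". The other rows cover vomiting, diarrhea, cardiac signs, alkaline phosphatase, creatinine, bilirubin, AST/ALT and QTc. Anemia does not appear.

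The recommended phase II dose is the "highest cohort level in which one or fewer subjects of 6 develops a first cycle DLT".

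Section 6.7 applies to "PHASE IB CYCLE 2+ AND PHASE II COMPONENTS". Its Table 6-4 has an anemia block. The grade 4 row, "Grade 4 Life-threatening consequences; urgent intervention indicated", carries the instruction to discontinue LEE011.

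The protocol treats anemia as hematologic throughout: it is listed in "Table 2-1 Hematologic AEs in study CLEE011X2101" (section 1.7.4) and again in Table 6-4. Section 9.1 names it among the grade 3 and 4 events suspected to be related to LEE011 for reporting purposes: "Anemia, febrile neutropenia, leukopenia, lymphopenia, neutropenia, thrombocytopenia".

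**The concern.** The first-cycle DLT count decides whether the next dose level opens and which dose goes into phase II. If a patient has a life-threatening anemia attributed to LEE011 in cycle 1 and nothing else that qualifies, the written rule scores that patient as DLT-free. Section 6.6 replaces only patients who never start LEE011, so the patient stays in the denominator. A level could then pass on a count that leaves out an event for which the same protocol requires the drug to be stopped once cycle 1 is over. With at most six patients per level in the written rules, one event can decide the outcome.

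**Working it through.** **Comparison of the tables.** Table 6-4 orders outright discontinuation at grade 4 for three hematologic events.

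| Grade 4 event | Table 6-4 (cycle 2+ and phase II) | Table 6.2 (cycle 1) |
|---|---|---|
| Thrombocytopenia | Discontinue | DLT |
| Febrile neutropenia | Discontinue | DLT |
| Anemia | Discontinue | No row; the catch-all does not apply |

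The discontinuation events for bilirubin, AST/ALT and QTc in Tables 6-5 and 6-6 also have DLT counterparts in Table 6.2. Grade 4 neutropenia is handled differently: Table 6-4 interrupts and reduces the dose, and Table 6.2 counts it only beyond 7 days. Leukopenia and lymphopenia have no row of their own in either table, so this comparison says nothing about them.

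A grade 4 anemia would still count through another row if it came with a related non-hematologic event of grade 3 or higher, a cardiac event, or thrombocytopenia with clinically significant bleeding. The gap concerns the isolated event.

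**Size.** The plan gives no figure to reproduce, so what follows is an illustration.

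Inputs:
- Rate of grade 4 anemia, *a*. Table 2-1 gives grade 3/4 anemia in 2 of 67 patients at 600 mg and does not split the grades, so grade 4 was 0, 1 or 2 of 67, that is 0, 1.5% or 3.0%. Using these as cycle 1, LEE011-related rates is an assumption. It ignores sampling error.
- Rate of all other DLTs, *d*: assumed 10% or 20%.
- Independence of the two: assumed.

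Formulas:
- DLT rate if grade 4 anemia counts: q = 1 - (1 - d)(1 - a). As written, q = d.
- A level clears under 3+3 (0 of 3, or 1 of 3 and then 0 of 3): (1 - q)³ + 3q(1 - q)⁵.
- At most 1 DLT in 6: (1 - q)⁶ + 6q(1 - q)⁵.

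Worked case, d = 0.10 and a = 0.03: q = 1 - 0.90 × 0.97 = 0.127.
- 3+3: 0.873³ + 3 × 0.127 × 0.873⁵ = 0.665 + 0.193 = 0.859. As written: 0.729 + 0.177 = 0.906.
- 1 of 6: 0.873⁶ + 6 × 0.127 × 0.873⁵ = 0.443 + 0.386 = 0.829. As written: 0.531 + 0.354 = 0.886.

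| d | a | q if counted | 3+3: as written → if counted | Difference (points) | 1 of 6: as written → if counted | Difference (points) |
|---|---|---|---|---|---|---|
| 10% | 0 | 0.100 | 90.6% → 90.6% | 0 | 88.6% → 88.6% | 0 |
| 10% | 1.5% | 0.1135 | 90.6% → 88.3% | 2.3 | 88.6% → 85.8% | 2.8 |
| 10% | 3.0% | 0.127 | 90.6% → 85.9% | 4.8 | 88.6% → 82.9% | 5.7 |
| 20% | 0 | 0.200 | 70.9% → 70.9% | 0 | 65.5% → 65.5% | 0 |
| 20% | 1.5% | 0.212 | 70.9% → 68.3% | 2.6 | 65.5% → 62.6% | 2.9 |
| 20% | 3.0% | 0.224 | 70.9% → 65.6% | 5.2 | 65.5% → 59.7% | 5.9 |

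Differences are taken before rounding. If half of the anemia cases counted through another row (assumption, *a* halved), the 3+3 differences fall to 0, 1.1 and 2.3 points at d = 10%, and to 0, 1.3 and 2.6 points at d = 20%.

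The documents give no anemia rate at 200 or 400 mg, so no figure is claimed for those levels.

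**The case against.** The strongest reply is that the gap is one of scoring and that other rules protect the patient.

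- A reader might infer that a patient with grade 4 anemia would stay on LEE011 through cycle 1. The documents do not support that. Section 6.5 ends treatment for "unacceptable toxicity or toxicity that results in treatment interruption of" more than 4 weeks, and also allows investigator discretion, in any cycle.
- Sections 6.6 and 9.4 contain a hard stop: two grade 4 events lasting at least 7 days, or two grade 5 events, at least possibly related to study treatment, end enrollment. It is not restricted by toxicity type, so it covers anemia.
- SAEs go to the DSMC within 2 working days (9.3.3), the DSMB may stop the trial (9.4), and escalation is reviewed in real time (16.0).
- The uncounted path is narrow. Patients enter with hemoglobin of at least 9.0 g/dl (5.1.10.3), active gastrointestinal bleeding is excluded (5.2.17), and a related bleed of grade 3 or higher already counts through the catch-all. In the palbociclib study of 23 HCC patients described in section 1.6, anemia is not among the grade 3 and 4 events named, though that list may not be complete.
- No stated rule says that every discontinuation event in Table 6-4 must be a DLT.

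These points stand and keep the weight low. They do not change the count. Stopping the drug under 6.5 does not make the event a DLT. The hard stop needs two events and, at grade 4, a duration of 7 days, so a single or short one passes. The committee reviews are discretionary and leave the written rule as it is. No reason is given for leaving anemia out while the other two hematologic events are matched.

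**Conclusion.** The gap is real on the text: a single, isolated, LEE011-related grade 4 anemia in cycle 1 is scored as no DLT for escalation and for the recommended phase II dose. Its effect is small and may be nil. The rise in the chance of clearing a level ranges from 0 to about 5 points under 3+3, and to just under 6 points under the 1-of-6 rule. All of this rests on assumed rates taken from 0-2 of 67 patients at 600 mg, on assumed other-DLT rates of 10-20%, and on independence. The figures are not upper bounds, because sampling error in so few events is ignored. They would be lower if some cases count through other rows.

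A reader might also infer that the selected dose will be unsafe, or that section 9.1 settles attribution. Neither follows. The numbers are too small for the first, and the 9.1 list serves reporting, so it shows only that the event is foreseen. The point is a cheap improvement to an inconsistent definition and not a flaw that invalidates the dose escalation.

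**What to change.** Add one row to Table 6.2: grade 4 anemia, possibly, probably or definitely related to LEE011. State in section 6.6 whether cohort 1 patients already treated are re-scored under the new row.

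No new tests are needed, since Table 7.1 already schedules a CBC at cycle 1 day 1, cycle 1 day 15 and cycle 2 day 1. The cost is a protocol amendment during escalation, with IRB approval before implementation (17.3), in a trial whose cohort 1 criteria were set after discussion with the FDA. There is also a slightly higher chance that a cohort is expanded or de-escalated.
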